1.5.2. Potential Benefits

This is the first study in which the efficacy and safety of up to 3 intravitreal injections of ocriplasmin in diabetic subjects with moderate to very severe NPDR will be assessed, and there may not be any direct benefit for the study participants.

An indirect benefit of study participation is that this study may contribute to the development of a drug that reduces the risk of disease progression to PDR. In addition, this study may realise overall advancement of medical and scientific knowledge that may benefit future patients. In addition, subjects will be closely followed up for DR progression while being in the study.

2. STUDY OBJECTIVE

- To assess the efficacy and safety of up to 3 intravitreal injections of ocriplasmin (0.0625mg or 0.125mg), in subjects with moderate to very severe NPDR, to induce total PVD in order to reduce the risk of disease progression to PDR

3. STUDY DESIGN AND METHODOLOGY

3.1. Study Endpoints

3.1.1. Efficacy Endpoints

Primary Efficacy Endpoint

- Total PVD by the Month 3 visit, confirmed on both B-scan ultrasound and SD-OCT (6mm), as assessed by the masked B-scan expert reader and the masked CRC, respectively

Exploratory Efficacy Endpoints

- A ≥ 2 -step progression on the International Clinical Diabetic Retinopathy Disease Severity Scale (ETDRS Severity Scale) from baseline, at Month 15 and at Month 24, based on 7-standard field stereo colour fundus photography, as assessed by the masked CRC
- Progression from NPDR at baseline to PDR (at least ETDRS level 61) at Month 15 and at Month 24, based on 7-standard field stereo colour fundus photography, as assessed by the masked CRC
- Improvement of ≥ 2 steps on the ETDRS Severity Scale from baseline, at Month 15 and at Month 24, based on 7-standard field stereo colour fundus photography, as assessed by the masked CRC
- Neovascularisation as compared to baseline, at Month 15 and at Month 24, based on 7-standard field stereo colour fundus photography, as assessed by the masked CRC
- Development or progression of macular oedema as compared to baseline, at each study visit, based on SD-OCT, as assessed by the masked CRC
- BCVA change from baseline at each study visit
- Total PVD at each study visit, confirmed on both B-scan ultrasound and SD-OCT (6mm), as assessed by the masked B-scan expert reader and the masked CRC, respectively
- Total PVD by the Month 3 visit, based on widefield SD-OCT, as assessed by the masked CRC, in a subset of sites where this is available
- Vitreous / pre-retinal haemorrhage by Month 24, based on 7-standard field stereo colour fundus photography, as assessed by the masked CRC
- Development of iris neovascularisation as compared to baseline, at each study visit, based on slit lamp examination
- PRP treatment by the Month 15 visit
- Anti-VEGF treatment by the Month 15 visit
- Vitrectomy by the Month 15 visit

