9.3.2. Procedure for Accounting for Missing, Unused and Spurious Data

All reasonable efforts will be made to obtain complete data for all subjects. However, missing observations may occur due to subjects lost to follow-up or to noncompliance with required assessments. Management of dropouts and missing data will depend on their frequency and the nature of the outcome parameter.

The primary analysis of the efficacy parameters will be performed on the Full Analysis Set using the last-observation-carried-forward (LOCF), unless otherwise specified. Sensitivity analysis to evaluate the robustness of the data will be performed using alternative imputation method on the Full Analysis Set and the Per Protocol Set.

In the safety analysis, missing data will not be replaced and data analysis will be performed based on the Observed Case (OC) imputation method.

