9.5.2. Exploratory Efficacy Analyses

The analysis of exploratory dichotomous endpoints will be similar to the methodology used for the primary endpoint. For each exploratory endpoint, the proportion of subjects who achieve the endpoint at a certain study visit will be calculated in each treatment arm with corresponding 95% CI, stratified for NPDR severity at baseline. The adjusted differences in proportions between sham and each of the ocriplasmin arms will be calculated with their corresponding 95% CIs and tested using the Cochran-Mantel-Haenszel test. In addition, the effect of treatment on the proportion of subjects who achieve the endpoint will be computed using a logistic regression with effects for treatment and NPDR severity at baseline. Mean change from baseline in ETDRS

letters will be calculated by treatment arms at follow-up visits, stratified for NPDR severity at baseline. The adjusted differences in means between treatment arms will be summarised and analysed using a PROC GLM model including factors for treatment, BCVA at baseline and NPDR severity at baseline.

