$$\text{floor}(\text{intck}(\text{'month'}, \text{DOB}, \text{first injection date}) - (\text{day}(\text{first injection date}) < \text{day}(\text{DOB}))) / 12$$

By Visit Layout

In tables summarizing data ‘By Visit’, post-injection 2 and 3 visits will be presented on 2 rows. The first row will be labelled ‘Day/Month xx, Post-Injection 2/3’ and will present data of subjects with 2 or 3 injections, respectively. The second row will be labelled ‘Day/Month xx, Missing Repeat Injection(s)’ and will present data of subjects who did not receive the complete set of repeat injections.

Early Termination Visit

The Early Termination visit corresponds to the last visit attended by subjects who discontinue from the study. Early Termination visits will be re-coded when possible. The related data will be summarized in the corresponding re-coded visit and in a visit named ‘*Early Termination*’. For example, if a subject discontinues with its last visit being the Day 28 visit, then the corresponding data will appear in the line ‘*Day 28, Post-Injection 1*’ and in the line ‘*Early Termination*’ of the summary tables.

Unscheduled Visit

Unscheduled visits will not appear in the summary tables, but in the listings.

Summary Statistics

Descriptive statistics for continuous variables and calculated change from baseline variables will include:

- number of subjects with available data
- mean and standard deviation
- median
- minimum and maximum

- 95% CI for mean, where indicated.

Categorical data and shift from baseline will be summarized by presenting:

- count
- percentage (where the denominator is based on the total number of subjects in the treatment group or overall, unless otherwise stated in the table footnotes)
- 95% CI for the proportion (Clopper-Pearson method), where indicated.

Protocol Deviations

Deviations from the protocol will be documented on an ongoing basis by the study monitors and project managers throughout the study. Protocol deviations are recorded outside the clinical database and will be reviewed by ThromboGenics during the course of the study, prior to database lock.

Missing Data

Missing data will not be replaced (unless otherwise specified), and data analysis will be performed based on the observed cases (OC) principle.

Subgroup Analysis

No subgroup analyses, nor analysis per center, will be performed.

Sensitivity Analysis

No sensitivity analyses will be performed.

Changes in Planned Analyses from the Protocol

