The early stopping of the subject enrolment has led to the following changes to the analyses planned in the protocol.

A single analysis dataset will be used instead of the 3 listed in the protocol.

The first and third quartiles, and 5th and 95th percentiles will not be included in the summary statistics of continuous variables.

No statistical testing will be performed.

The last-observation-carried-forward method for data imputation will not be used, and no sensitivity analysis will be performed.

The stratification variable, NPDR severity, will not be taken into account in any summary statistics.

The following exploratory endpoints will not be summarized:

- $A \geq 2$ -step progression on the ETDRS Severity Scale from baseline, at Month 15 and at Month 24, based on 7-standard field stereo colour fundus photography, as assessed by the masked CRC

- Improvement of ≥ 2 steps on the ETDRS Severity Scale from baseline, at Month 15 and at Month 24, based on 7-standard field stereo colour fundus photography, as assessed by the masked CRC
- Neovascularisation as compared to baseline, at Month 15 and at Month 24, based on 7 standard field stereo colour fundus photography, as assessed by the masked CRC
- Vitreous / pre-retinal haemorrhage by Month 24, based on 7-standard field stereo colour fundus photography, as assessed by the masked CRC
- Development of iris neovascularisation as compared to baseline, at each study visit, based on slit lamp examination

4. Appendix

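### CRC-confirmed PDR before Month 15 or Month 24 has no visible route into the Month 15/24 proportion if the subject then withdraws; a cumulative count beside it would close the gap

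*Protocol*

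**What the plan says.** Protocol section 3.1.1 lists among the exploratory endpoints "Progression from NPDR at baseline to PDR (at least ETDRS level 61) at Month 15 and at Month 24", graded by the masked central reading centre (CRC) from seven-field photographs. Section 9.5.2 gives the matching analysis for binary endpoints: "the proportion of subjects who achieve the endpoint at a certain study visit will be calculated in each treatment arm". In section 3.1.1 other endpoints are cumulative, worded as *by* a visit: the primary endpoint, haemorrhage, PRP, anti-VEGF and vitrectomy.

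Section 7.2.3 schedules photographs for everyone at screening, Month 15 and Month 24 or exit. At Months 3 and 9 they are taken only when the investigator suspects PDR. Section 5.18 allows unscheduled visits at any time and requires their results to be recorded. Section 6.4.1.1 permits PRP, without requiring it, once the CRC has confirmed PDR.

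On missing data, protocol section 9.3.2 planned: "The primary analysis of the efficacy parameters will be performed on the Full Analysis Set using the last-observation-carried-forward (LOCF), unless otherwise specified". The SAP replaces this. Under Changes in Planned Analyses from the Protocol: "The last-observation-carried-forward method for data imputation will not be used, and no sensitivity analysis will be performed". Under Missing Data: "Missing data will not be replaced (unless otherwise specified), and data analysis will be performed based on the observed cases (OC) principle". Under Unscheduled Visit: "Unscheduled visits will not appear in the summary tables, but in the listings". Under Summary Statistics the percentage is one "where the denominator is based on the total number of subjects in the treatment group or overall, unless otherwise stated in the table footnotes". Under Early Termination Visit: "Early Termination visits will be re-coded when possible"; that data also goes into a separate Early Termination row.

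Progression to PDR is not on the SAP's list of endpoints no longer summarised, so it stays in the final analysis.

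**The concern.** Whether a subject has reached PDR is naturally a question about what has happened up to a given time. Here it is answered by a grade at one visit. A subject whose PDR the CRC has already confirmed, and who then leaves, has no grade at Month 15 or 24. The carry-forward rule that might have kept such a case in the count has been withdrawn, and nothing in the public text replaces it.

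The stated objective (protocol section 2) is to induce total PVD in order to lower the risk of progression to PDR. Section 3.1.1 has five endpoints read from fundus photographs, and the SAP drops four. The PDR row is therefore the only photograph-based summary left, in a trial that randomised 48 of 115 planned subjects. One event left out of a small arm is visible in the percentage a reader will look at.

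**Working it through.** The documents give no PDR rate, event count or drop-out rate after Month 3, so there is no plan figure to reproduce. The sample-size statement concerns total PVD by Month 3 and plays no part here. The check is a trace of one subject, then a scale.

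**Trace.** A subject is photographed on suspicion at Month 9, the CRC grades level 61 or above, and the subject withdraws.

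1. Protocol sections 3.1.1 and 9.5.2: the Month 15 and Month 24 proportions need a grade at those visits. There is none.
2. Protocol section 9.3.2: carry-forward could have taken the Month 9 grade into both rows. The SAP removes it.
3. SAP, Early Termination Visit: its worked example puts a subject whose last visit is Day 28 in the Day 28 row and the Early Termination row. By analogy this subject appears at Month 9 and under Early Termination, not at Month 15 or 24.
4. SAP, Summary Statistics: with the default denominator the subject stays below the line and is absent above it, which reads as no progression. If a table footnote restricts the denominator to graded subjects, the subject leaves both.

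Protocol Table 6 has no scheduled visit between Months 9 and 15 or between Months 15 and 24. Confirmation in those gaps would need unscheduled photographs, which the SAP lists but does not summarise.

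**Inputs for scale.** 48 randomised (Clarification Note) at 2:2:1 (protocol section 3.2). Assumed: all were treated and the split is close to nominal. 48 × 2/5 = 19.2 and 48 × 1/5 = 9.6, so about 19/19/10.

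**One omitted event, whole-arm denominator.**

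- Ocriplasmin arm: 1/19 = 5.3 points (1/20 = 5.0).
- Sham: 1/10 = 10.0 points (1/9 = 11.1).
- Change in sham minus ocriplasmin: −10.0 for one sham event, +5.3 for one ocriplasmin event, −10.0 + 5.3 = −4.7 for one in each.

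**Example in one arm of 19** (assumed: three subjects ever confirmed, one of whom withdraws). Cumulative count: 3/19 = 15.8% (Clopper-Pearson 95% CI 3.4 to 39.6). At-visit count: 2/19 = 10.5% (1.3 to 33.1), or 2/18 = 11.1% among those graded.

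**Observed-case denominator, two arms** (assumed truth 4/10 against 4/19, difference 40.0 − 21.1 = 18.9 points).

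- One PDR subject leaves each arm: 3/9 − 3/18 = 33.3 − 16.7 = 16.7.
- One non-PDR subject leaves each arm: 4/9 − 4/18 = 44.4 − 22.2 = 22.2.

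The difference can move either way, so no direction follows.

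**The case against.** The best defence is that a fixed-visit endpoint is a sound choice. Only Months 15 and 24 have follow-up photographs planned for everyone still in the study; earlier ones depend on suspicion. Scoring at those visits gives uniform ascertainment, and the protocol uses *by* elsewhere, so *at* looks deliberate. This stands, and it is why the at-visit summary should stay. It does not settle what happens to a confirmed case that then withdraws.

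Second, SAP section 1 says the public version leaves out mock-up tables and some content, and the SAP's missing-data and denominator rules allow stated exceptions. A derivation rule could sit there. This also stands: the point is about the public text.

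Third, several provisions recover cases. Section 4.2.2 asks for Exit Visit procedures, which include photographs, whenever possible. Early Termination data are tabulated. PRP is counted cumulatively to Month 15. These narrow the gap, but none is a count of subjects who reached PDR.

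A reader might infer more than the documents support:

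- *That earlier PDR appears in no table.* Months 3 and 9 are scheduled visits, and nothing in the SAP bars their grades from by-visit or Early Termination rows.
- *That treatment after Month 15 is lost.* The SAP's concomitant-intervention category starts at the first injection and has no Month 15 cut-off.
- *That dropping carry-forward hides eyes later graded below level 61.* Carry-forward fills missing values and would not override an observed grade. Such an eye would fall out of an at-visit count under either plan, but no passage shows that this occurs.

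**Conclusion.** The point holds in a limited form. Under the public protocol and SAP, PDR confirmed at Month 3, Month 9 or an unscheduled visit is not counted in the Month 15/24 proportion if the subject then withdraws. With the default denominator that subject is treated as not having progressed.

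The scale of 5.3 or 10.0 points per omitted event rests on assumed arm sizes and is simply one over the arm size. The number of such events, the arm they fall in and the direction of any effect cannot be derived, so a claim of bias for or against ocriplasmin would be unsupported. The endpoint is exploratory, no test is performed, and total PVD by Month 3 is untouched. Severity is the lowest grade, a cheap improvement; confidence is medium because the table shells are not public.

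**What to change.** Keep the at-visit summary. Beside it, add one descriptive table: the number and percentage of treated subjects with any CRC grade of level 61 or above, at a scheduled or unscheduled photograph, by Month 15 and by Month 24, whatever happened afterwards, with all treated subjects as the denominator. If the full SAP already contains this, it is enough to say so.

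Footnote that Month 3, Month 9 and unscheduled photographs were not systematic. Label the table post hoc if it is added after the sponsor was unmasked at the Month 15 analysis (protocol section 3.6.1). SAP section 1 already describes the final analysis in the past tense, so the label would very likely be needed.

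Separate tables of PRP, anti-VEGF and vitrectomy by Month 24 are needed only if the SAP's concomitant-intervention output does not already cover them.

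The cost is one table definition and its programming; the grades are already collected and unscheduled results must be recorded. The downside is that the cumulative count mixes systematic with suspicion-triggered photographs, and it is a minimum, since PDR that was never photographed stays uncounted. No clinical rule changes.

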3.1.2. Safety Endpoints

Principal Safety Endpoint

[figure not shown]
- Ocular TEAEs in the study eye

Other Safety Endpoints

Safety will be further assessed through reported TEAEs, full ophthalmic examination, BCVA assessment, assessment of colour vision (in a subset of sites where the Roth 28 Colour Test is available), SD-OCT, ffERG (at sites where this is available, in approximately 25% of the subjects) and assessment of immunogenicity.

3.2. Study Design Overview

Figure 1: Study Design Overview

Light grey highlighted visits indicate visits with ocriplasmin/ sham injection.

^a All subjects assigned to the ocriplasmin arms will receive an intravitreal injection of ocriplasmin 0.0625mg or 0.125mg at Day 0. These subjects will be re-treated with the same dose of ocriplasmin at Day 35 and at Day 70 if, by that time, they have not achieved total PVD on both B-scan ultrasound and SD-OCT, as assessed by the masked B-scan expert reader and the masked CRC, respectively. Subjects who have total PVD on both B-scan ultrasound and SD-OCT will receive subsequent sham injection(s) in place of ocriplasmin injection(s).

^b Subjects assigned to the sham arm will receive 3 sham injections at Day 0, Day 35 and Day 70.

* The masked Investigator / designee will make a **scripted phone call** to each subject 24-72 hours after the injection visit. Based on this phone call, the subject may be invited back for an unscheduled study visit, as per the masked Investigator's clinical judgement.

- **Study design.** Multi-centre, randomised, sham-controlled, double-masked, Phase 2 clinical study with 3 parallel treatment arms
- **Study arms and treatments.**
 - **Ocriplasmin 0.0625mg arm.** Approximately 46 subjects will receive up to 3 intravitreal injections of ocriplasmin 0.0625mg, approximately 1 month apart. All subjects assigned to this arm will receive an intravitreal injection of ocriplasmin 0.0625mg at Day 0. These subjects will be re-treated with ocriplasmin 0.0625mg at Day 35 and at Day 70 if, by that time, they have not achieved total PVD on both B-scan ultrasound and SD-OCT, as assessed by the masked B-scan expert reader and the masked CRC, respectively. Subjects who have total PVD on both B-scan ultrasound and SD-OCT will receive subsequent sham injection(s) in place of ocriplasmin injection(s).

- **Ocriplasmin 0.125mg arm.** Approximately 46 subjects will receive up to 3 intravitreal injections of ocriplasmin 0.125mg, approximately 1 month apart. All subjects assigned to this arm will receive an intravitreal injection of ocriplasmin 0.125mg at Day 0. These subjects will be re-treated with ocriplasmin 0.125mg at Day 35 and at Day 70 if, by that time, have not achieved total PVD on both B-scan ultrasound and SD-OCT, as assessed by the masked B-scan expert reader and the masked CRC, respectively. Subjects who have total PVD on both B-scan ultrasound and SD-OCT will receive subsequent sham injection(s) in place of ocriplasmin injection(s)
- **Sham arm.** Approximately 23 subjects will receive 3 sham injections, approximately 1 month apart. All subjects assigned to this arm will receive a sham injection at Day 0, Day 35 and Day 70
- **Test product, dose and mode of administration.** Up to 3 intravitreal injections of ocriplasmin 0.0625mg or ocriplasmin 0.125mg
- **Reference therapy (comparator), dose and mode of administration.** 3 sham injections
- **Treatment allocation.** Eligible subjects will be sequentially assigned according to a computer-generated randomisation list to the ocriplasmin 0.0625mg arm, the ocriplasmin 0.125mg arm or the sham arm in a 2:2:1 allocation ratio. Randomisation will be stratified by baseline NPDR severity (moderate and moderately severe, *i.e.* ETDRS Level 43A-47D *vs.* severe and very severe NPDR, *i.e.* ETDRS Level 53A-E). It is expected that more subjects with moderate and moderately severe than with severe and very severe NPDR will be enrolled, as a reflection of the natural population. Therefore, enrolment in the moderate and moderately severe NPDR stratum may become capped in the course of the study
- **Study duration.** For each subject enrolled, the study duration will be approximately 24 months from the first injection

3.3. Number of Subjects

Approximately 115 subjects are planned to be enrolled (approximately 46 in each ocriplasmin arm and 23 in the sham arm). For a detailed description of the sample size determination, refer to [Section 9.1](#).

3.4. Data Monitoring Committee

In order to maintain a general safety oversight and to monitor the risk / benefit balance, a DMC will be established for this study.

From the time the first subject is injected until the last subject completed the Month 3 visit (Visit 8), the following TEAEs will be escalated to the DMC on an ongoing basis:

- Lens subluxation
- Iso-electric ffERG

- Clinically significant increased intraocular inflammation after repeat (2nd or 3rd) injection
- BCVA decrease \geq 15 letters from baseline, without evidence of resolution or stabilisation within 24 hours
- Foveal detachment or worsening of a foveal detachment
- Any other event at the discretion of the Sponsor

The DMC will conduct periodic reviews at the following pre-defined timepoints:

- After approximately 20% of the subjects completed the Month 2 visit (Visit 6b)
- After approximately 50% of the subjects completed the Month 3 visit (Visit 8)
- After all subjects completed the Month 3 visit (Visit 8)
- After all subjects completed the Month 15 visit (Visit 10)

In addition, *ad hoc* DMC meetings may be organised.

The DMC will be empowered to make recommendations to the Sponsor on further study conduct. Such recommendations include continuing or terminating the study or modifications to the study. Another recommendation may be temporary suspension of enrolment and / or study treatment until some uncertainty is resolved.

The DMC responsibilities and procedures will be documented in the DMC Charter.

